9.4.5 BASELINE DESCRIPTIVE STATISTICS

Baseline characteristics (e.g., demographics, oncologic details, behavioral characteristics) for the NDURE and Usual Care arms will be summarized, and descriptive statistics calculated. Median follow-up overall and by trial arm will be calculated using a reverse Kaplan-Meier estimator.

9.4.6 PLANNED INTERIM ANALYSES

N/A

9.4.7 SUB-GROUP ANALYSES

Planned sub-group analyses of the primary endpoint will occur based on age and sex to evaluate the impact of inclusion across the lifespan and sex as biologic variables. Historical data have not established an association between either age or sex with the primary endpoint⁶. Given the importance of race to the study objectives, analysis of the primary endpoint by race is evaluated as a secondary objective instead of planned subset analysis. Additional planned subset analyses will evaluate the impact of the NDURE intervention on the primary endpoint based on insurance status and fragmentation of care between the surgical facility and radiation facility, both of which have been described as risk factors for delayed PORT⁶. As such, both of these variables have the potential to confound the effect of the intervention were they to be imbalanced in a future RCT. As such, evaluating their impact on the primary endpoint in this study would allow for rational stratification in planned future RCTs.

9.4.8 TABULATION OF INDIVIDUAL PARTICIPANT DATA

Individual participant data will not be listed by measure and time point.

9.4.9 EXPLORATORY ANALYSES

For other exploratory endpoints (e.g., health behavior constructs), data will be summarized using frequency and percent for categorical variables and using mean, median, standard deviation, IQR and range for continuous variables. We will construct 90% CIs to provide a measure of uncertainty in estimated proportions and means. Comparisons between trial arms of other exploratory endpoints will be performed using *t*-tests and chi-square tests, or Wilcoxon rank sum and Fisher's exact tests as appropriate. Pre- and post-intervention values of variables measuring the theoretical constructs underlying NDURE (i.e. care coordination, self-efficacy in cancer care, support, and knowledge) will be compared using Wilcoxon sign rank tests. Comparisons between arms of the change in scores will be conducted using Wilcoxon rank sum tests.

For the exploratory endpoints of barrier reduction and unresolved barriers, we will calculate the proportion of unresolved barriers and the frequency of unresolved barriers (respectively) at the end of NDURE, consistent with prior PN studies⁵¹. We will use logistic regression to assess the association between unresolved barriers and the rate of PORT delay (primary endpoint), controlling for randomization stratification variables.

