6.3 MEASURES TO MINIMIZE BIAS: RANDOMIZATION AND BLINDING

Bias will be minimized through stratified sampling and a stratified randomized permuted block design. We will use a stratified sampling approach to achieve a fixed sample size for AA patients (n=25 in each arm) to ensure that we 1) achieve racial balance between the NDURE and UC arms, and 2) oversample AA relative to their frequency in the study population. Oversampling AAs is key for the study design because of the prognostic significance of AA race with delayed PORT initiation^{6,45}. We will then use a stratified randomization scheme, with randomization at the individual patient level using a 1:1 allocation ratio. Strata will be defined by predicted location of radiation facility (MUSC, non-MUSC) because of the known association of this variable with PORT delay^{6,45}. As such, our design balances by key potential confounders across trial arms. Patients will be randomized 1:1 to NDURE or usual care using a permuted block randomization method, with randomly selected block sizes of 2 or 4. Given the impossibility of delivering the NDURE intervention in a non-blinded fashion, allocation concealment will be non-blinded. The study statistician will generate and implement the randomization schema and randomization list. The study coordinator will implement the randomization.

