9.4.3.2 RCT OF NDURE VERSUS USUAL CARE

For the primary endpoint (delays starting PORT as defined in **Section 8.4, Endpoint and Other Non-Safety Assessments**), the difference in PORT delay comparing NDURE to UC will be evaluated using a model-based approach to accommodate adjustment for randomization stratification variables. Specifically, we will use a binary regression generalized linear model (GLM) with identity link to model the probability of PORT delay as a function of treatment arm and randomization stratification variables (race and predicted location of radiation facility). We adopt this approach as opposed to a logit model or Mantel-Haenzel (MH) type approach since the estimand is the population average treatment effect, whereas the odds ratio is not collapsable and therefore inference based on logistic regression or MH estimation would be limited to a conditional treatment effect. (Additional details can be found in the FDA Guidance Document on Adjusting for Covariates in Randomized Clinical Trials.) The risk difference (PORT delay rate in UC – PORT delay rate in NDURE) will be estimated based on the treatment effect slope parameter. We will report the corresponding model-based 90% CI and two-sided p-value. We will additionally report model-based PORT delay rates for each trial arm with corresponding 90% CIs. Should GLM convergence be an issue, we will adopt an alternative approach based on subject-level predicted probabilities of PORT delay from a logistic model as outlined by Freedman⁶² and by Steingrimsson.⁶³ Analysis will be performed using the PORT delay analysis set.

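### The exploratory arm comparisons leave out the factors that randomization balances, which costs precision wherever those factors predict the endpoint

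*Combined protocol and SAP*

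**What the plan says.** Section 9.4.9: "Comparisons between trial arms of other exploratory endpoints will be performed using" t-tests and chi-square tests, or Wilcoxon rank sum and Fisher's exact tests. For pre-to-post questionnaire scores, "Comparisons between arms of the change in scores will be conducted using Wilcoxon rank sum tests". Neither sentence mentions a stratum. On intervals, the section says only "We will construct 90% CIs to provide a measure of uncertainty in estimated proportions and means"; it specifies none for a difference between arms.

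Section 6.3 gives the design. "Strata will be defined by predicted location of radiation facility (MUSC, non-MUSC"), with 1:1 permuted blocks "with randomly selected block sizes of 2 or 4". Stratified sampling is used to "achieve a fixed sample size for AA patients (n=25 in each arm"). Section 9.4.3.2 treats both factors as "randomization stratification variables (race and predicted location of radiation facility").

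Elsewhere the plan uses these factors. The primary risk-difference model (9.4.3.2) and the stratified log-rank tests, Cox models and binary models (9.4.4.2) adjust for them. One exception is the three binary care-process endpoints in 9.4.4.2, which fall back to unadjusted rates and a z-test if the model does not converge. Within 9.4.9, only the logistic model relating unresolved barriers to PORT delay is fitted "controlling for randomization stratification variables". Section 9.2.2 states that covariate adjustment preserves the type I error rate and gains power over an unadjusted model.

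**The concern.** Blocking within strata removes between-stratum variation from the actual sampling error of the arm difference. A test that ignores the strata still counts that variation in its standard error. If facility or race predicts the endpoint, the test then rejects less often than its nominal level and has less power than the design provides.

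The endpoints affected are exploratory, but the plan puts some to use. The amendment history (10.4) says that the endpoints added in version 6.0, PORT duration and completion of intended PORT among them, respond to a worry that a faster start could lead to breaks during radiation. For a possible harm, a conservative test is not the cautious choice, because it makes a real signal easier to miss. Section 4.2.2 relies on the behavioral-mechanism data, which include CTM-15, to limit concern about non-specific effects.

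**Working it through.** **The plan's own figure.** Section 9.2.2 states 83% power for 45% versus 25%, 75 per arm, pooled Z-test, two-sided alpha 0.1. Pooled SE = sqrt(2 × 0.35 × 0.65 / 75) = 0.0779. SE under the alternative = sqrt((0.45 × 0.55 + 0.25 × 0.75) / 75) = 0.0762. Power = Phi((0.20 − 1.645 × 0.0779) / 0.0762) = 82.7%, so the figure reproduces. The plan states no figure for the exploratory comparisons.

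**Inputs for the exploratory tests.** 75 per arm is from 9.2.2. Two equal facility strata are assumed; section 2.2.5 reports care across healthcare systems in 51% of cases as background. The facility difference d, in within-stratum SDs, is not in the documents and is varied from zero.

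**Formulas.** With arms balanced in two equal strata whose means differ by d, the outcome variance is 1 within strata and 1 + d²/4 overall.
- Ratio r of unadjusted to stratified SE = sqrt(1 + d²/4)
- True size at nominal 10% = 2 × (1 − Phi(1.645 r)); at nominal 5%, use 1.960
- Stratified SE = sqrt(2/75) = 0.1633, so a 0.4 SD arm effect lies 0.4 / 0.1633 = 2.449 SEs from zero
- Unadjusted power at nominal 10% = Phi(2.449 − 1.645 r); stratified power = Phi(2.449 − 1.645) = 79%

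| Facility difference d | SE too large by | True size, nominal 10% | Unadjusted power | Stratified power |
|---|---|---|---|---|
| 0 | 0% | 10.0% | 79% | 79% |
| 0.2 SD | 0.5% | 9.8% | 79% | 79% |
| 0.3 SD | 1.1% | 9.6% | 78% | 79% |
| 0.5 SD | 3% | 9.0% | 77% | 79% |
| 0.8 SD | 8% | 7.6% | 75% | 79% |
| 1.0 SD | 12% | 6.6% | 73% | 79% |

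Section 9.4.1 pairs a p-value of 0.05 with 90% CIs. At a nominal 5%, the sizes for 0.5, 0.8 and 1.0 SD are 4.3%, 3.5% and 2.8%.

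**Binary case.** The ratio is sqrt(p(1 − p) / mean of the within-stratum p(1 − p)), with p the overall rate. For an assumed completion of 95% at MUSC and 85% elsewhere: sqrt(0.0900 / 0.0875) = 1.014, true size 9.5% at nominal 10%. For an assumed 95% and 70%: sqrt(0.1444 / 0.1288) = 1.059, true size 8.2%.

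**Check by simulation.** Null data were generated for 150 patients (50 AA, 100 white; 51% outside facility assumed) in permuted blocks of 2 or 4, with R² the share of outcome variance explained by race and facility together.
- With blocking on both factors, the unadjusted t-test rejected 10.0%, 8.5%, 6.9% and 5.4% of the time at nominal 10%, for R² of 0, 0.10, 0.20 and 0.30. Wilcoxon results were close to these.
- The model adjusted for race and facility stayed at 9.5% to 10.6% for every R² tried (0 to 0.30).
- With blocking on facility only, the unadjusted sizes were 9.6% (R² 0.10) and 8.7% (R² 0.20), so the conservatism is weaker if race is not itself blocked.
- Fisher's test rejected 7.4% at nominal 10% even with equal rates in all strata, so part of its conservatism is not due to the strata.

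The table and the simulation agree: d of 1.0 corresponds to R² = 0.25 / 1.25 = 0.20, and the sizes are 6.6% by formula and 6.9% by simulation.

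**The case against.** The strongest reply is that nothing here is shown to be prognostic. The documents tie facility and race to PORT delay (6.3), not to questionnaire scores, PORT duration or PORT completion. If the strata do not predict an endpoint, the unadjusted test holds its level and loses nothing; at 0.2 to 0.3 SD the loss is about 1% in the standard error. The tests do not inflate false positives, no decision rule rests on these endpoints, and simple unadjusted comparisons are defensible in a single-site pilot. The adjusted logistic model in 9.4.9 estimates an association, so it is not a precedent for adjusted arm comparisons.

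All of that stands, and it makes the point conditional. There are still grounds to expect some association: CTM-15 measures care integration (8.4.7), and Figure 3 lists fragmentation across organizations as a determinant of timely PORT. That is plausibility, not evidence of size.

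Three stronger readings are not supported. A reader might infer that the stated 90% CIs over-cover. Those in 9.4.9 are for proportions and means, so excess width concerns only an interval for the arm difference, which that section does not specify. A reader might infer that the loss amounts to discarding 20% of patients at 1.0 SD. That follows from interval width (1 − 1/1.25 = 20%). Matched on power, it is 1 − ((1.645 + 0.610) / 2.449)² = 15%. Finally, a reader might extend the point to the barrier counts. Those have their own paragraph in 9.4.9, which describes only their calculation, so whether these tests apply to them is unclear.

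**Conclusion.** The point holds as a conditional gain in precision, not as an error that invalidates the tests. The exploratory arm comparisons omit factors that the design balances and that the primary and secondary models use, and the plan gives no reason for the difference. The cost ranges from nothing, if the strata do not predict the endpoint, to 6 percentage points of power (79% to 73%) at an assumed 1.0 SD facility difference. It becomes material only towards the upper end of that range.

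These sizes rest on 75 per arm, an even facility split, balanced arms within strata and an assumed strength of association. Section 9.4.2 prescribes complete-case analysis for exploratory endpoints, and PORT duration is defined only in patients who complete the course, so actual numbers may be lower. This is a desirable refinement.

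**What to change.** In 9.4.9, state that between-arm comparisons adjust for race and predicted radiation facility, as follows.

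- Scores, change scores and durations: a linear model with arm, race and predicted facility, or the van Elteren stratified rank-sum test where a rank method is preferred.
- Binary endpoints such as PORT completion: the identity-link model already used in 9.4.3.2 and 9.4.4.2. If it does not converge, use the standardised-logistic fallback of 9.4.3.2. Use a stratified exact or CMH test when counts are sparse.
- Report the adjusted arm difference with a 90% CI.

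If the team prefers to keep the simple tests, label these comparisons unadjusted and descriptive.

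The cost is a few sentences in the plan and a few lines of code. Race (8.2.1) and predicted facility (8.2.2) are already recorded at baseline, so no new data are needed.

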1.3 SCHEDULE OF ACTIVITIES

Table 1. Schedule of Activities for NDURE and Usual Care: Screening, Treatment, and Follow-up								
Study Period		Screening	Allocation	Treatment			Follow-Up	
Visit Label	Visit #			Pre -Op	Pre - D/ C	Post - D/C		
Visit Label	Visit #	1	--	2	3 ^{a,b}	4 ^c	5 ^d	6 ^e
Study Activity								
Enrollment	Eligibility Screen	X						
	Informed Consent	X						
Allocation	Allocation		X					
Study Intervention	NDURE			X	X	X	X	
	Usual Care			X	X	X	X	
Study Assessments								
Baseline	Demographics	X						
	Baseline Oncologic Characteristics	X						
	Charlson-Deyo Comorbidity Index	X						
	PORT Delay Nomogram	X						
	Lukwago Cultural Questionnaire	X						
Safety	Adverse Events			←		→		
Efficacy	Surgical Details				X			
	PORT Start Date						X	
Fidelity	NDURE Fidelity						X	
Feasibility	NDURE Accrual	X						
	NDURE Completion			X	X	X	X	
	Navigator Caseload			←		→		
	Navigator Time Allocation			X	X	X	X	
Acceptability	PSN-I Questionnaire						X	
	Semi-Structured Interview						X	
	Program Evaluation Questionnaire						X	
Barriers to Timely PORT	PBQ-Patient Questionnaire			X	X	X	X	
	PBQ-Navigator			X	X	X	X	
	Presurgical RT Consult						X	
	Pre-RT Dental Extractions						X	

Table 1. Schedule of Activities for NDURE and Usual Care: Screening, Treatment, and Follow-up								
Study Period		Screening	Allocation	Treatment			Follow-Up	
Visit Label	Visit #			Pre-Op	Pre-D/C	Post-D/C		
		1	—	2	3 ^{a,b}	4 ^c	5 ^d	6 ^e
Study Activity								
Cancer Care Delivery Processes	Date Pathology Report Returned						X	
	Date of Postoperative Referral to Radiation Oncology						X	
	Date of Postop Appointment with Radiation Oncology						X	
	Date of CT Simulation						X	
Adjuvant Therapy Details	Type of Adjuvant Therapy						X	
	PORT Completion Date						X	
	Radiation and Medical Oncology Facility						X	
Health Behavior Constructs	CTM-15 Questionnaire				X	X		
	ISEL-12 Questionnaire	X					X	
	PSQ Questionnaire	X			X	X		
	IPQ-R Consequences Questionnaire	X			X	X		
	CASE-Cancer Questionnaire	X					X	

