To explore the preliminary impact of NDURE compared with UC on completion of adjuvant therapy	PORT duration, defined as the number of days from the initiation of PORT to the completion of PORT among patients who complete the intended course of adjuvant therapy.
	Completion of intended course of PORT, defined as receipt of the planned PORT dose (total Gy)
To explore the preliminary clinical impact of NDURE compared with UC on decreasing barriers to timely PORT.	Percent of total barriers on PBQ that are resolved
	Number of unresolved barriers on PBQ
	Reason for PORT delay
To explore the preliminary behavioral mechanism of action of NDURE.	CTM-15 scale score
	Change from baseline in 
 ISEL-12 scale score Perceived Susceptibility scale score IPQ-R Consequences scale score CASE-Cancer scale score

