8 STUDY ASSESSMENTS AND PROCEDURES

8.1 SCREENING PROCEDURES

Once a subject has signed the ICF, an identification number will be assigned to him/her and the study related screening procedures will start. A subject will be randomized into the study after he/she has signed the ICF and all eligibility criteria have been met.

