9.2.2 RCT OF NDURE VERSUS USUAL CARE

Power and sample size calculations were performed using PASS v08.0.13, “Inequality Tests for Two Independent Proportions.” The primary endpoint for this pilot RCT is the rate of PORT delay, defined as starting PORT > 6 weeks after surgery. Our primary objective is to compare PORT delay rates between the NDURE and usual care arms. We hypothesize that, compared with patients who receive usual care, patients who receive NDURE will have a decreased rate of PORT delay (initiation of PORT > 6 weeks after surgery). Alternatively, our null hypothesis is that there will be no difference in the rate of PORT delay between NDURE and usual care. We assume the rate of PORT delay in the usual care arm will be 45%⁴⁵ and target an absolute reduction in PORT delay of 20% (rate of PORT delay in the NDURE arm = 25%)²⁴. This effect size is clinically significant and realistic given results in similar (non-randomized) interventions²⁴. Seventy-five patients in each arm yields 83% power to detect a 20% reduction in PORT delay (45% versus 25%) based on a two-sided Z-test with pooled variance of two independent proportions assuming a two-sided $\alpha = 0.1$. Our selection of $\alpha = 0.1$ and $1 - \beta = 0.8$ is based on the desire to emphasize power over type I error at this early stage of development (single-site pilot RCT) to ensure follow-up on promising interventions. Furthermore, given the trial’s design, comparison of PORT delay rates between

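### Section 9.4.9 compares health-behavior change scores by unadjusted rank-sum tests, although a pre-randomization baseline would allow a usually more precise adjusted analysis

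*Combined protocol and SAP*

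**What the plan says.** Table 2 in Section 3 lists, among the exploratory objectives, "To explore the preliminary behavioral mechanism of action of NDURE". Its endpoints are the CTM-15 score and, under the words "Change from baseline in", four scales: ISEL-12, Perceived Susceptibility, IPQ-R Consequences and CASE-Cancer. For the comparison of arms, Section 9.4.9 states: "Comparisons between arms of the change in scores will be conducted using Wilcoxon rank sum tests". No covariates are named for it.

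The schedule of activities (Section 1.3) marks all four scales at Visit 1, the screening column that precedes allocation. Section 8.1 confirms the order: "A subject will be randomized into the study after he/she has signed the ICF and all eligibility criteria have been met". As far as the table columns can be read, ISEL-12 and CASE-Cancer are repeated once, at Visit 5, while Perceived Susceptibility and IPQ-R are repeated at both Visit 3 and Visit 4. CTM-15 is marked only at Visits 3 and 4, so it has no baseline.

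Elsewhere the plan does adjust. Section 9.2.2 argues that including the stratification variables raises power. Section 9.4.3.2 adjusts the primary analysis for race and predicted radiation facility, and the second paragraph of Section 9.4.9 controls for the stratification variables when it relates unresolved barriers to PORT delay.

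**The concern.** A covariate measured before randomization is available for each of these four scales, and the plan uses it only by subtraction. Subtraction fixes the baseline coefficient at 1, while the coefficient that minimizes variance is usually smaller. The contrast is then noisier than it need be, and part of any chance baseline difference between arms passes into the change contrast.

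What is at stake is modest but specific. Section 4.2.2 defends the usual-care control partly on the ground that the mechanism data will limit worry about nonspecific effects. (That section calls the mechanism objective secondary; Table 2 and the synopsis class it as exploratory, and it is treated as exploratory here.) Section 9.4.2 restricts exploratory endpoints to complete cases, so missing questionnaires reduce the information further. Section 9.4.9 provides intervals for estimated means and proportions but does not specify one for the between-arm difference.

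**Working it through.** **The plan's own figure.** No power, SD, effect size or correlation is given for these scores. The only power statement concerns PORT delay: 75 per arm, 45% versus 25%, two-sided alpha 0.1, by a "two-sided Z-test with pooled variance of two independent proportions". The pooled rate is 0.35, so z = [0.20 × √75 − 1.645 × √(2 × 0.35 × 0.65)] / √(0.45 × 0.55 + 0.25 × 0.75) = (1.732 − 1.110) / 0.660 = 0.944. Power is 82.7%, which agrees with the stated 83%. It does not bear on the scores; only the 75 per arm and alpha 0.1 are borrowed below for illustration.

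**Variance ratio.** Let rho be the baseline-to-follow-up correlation and r the follow-up SD divided by the baseline SD. In units of baseline variance, the arm contrast has variance proportional to

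- change score: 1 + r² − 2·rho·r
- baseline-adjusted: r²(1 − rho²)

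With r = 1 the ratio, adjusted over change, is (1 − rho²) / [2(1 − rho)] = (1 + rho)/2. This applies to a comparison of means. Under normality a rank-sum test has relative efficiency 0.955 against the t-test, so the ratio against the planned test is 0.955 × (1 + rho)/2. The power columns assume an effect of 0.4 SD. Both rho and the effect size are assumptions.

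| rho (assumed) | ratio vs mean change | ratio vs rank-sum on change | power, rank-sum on change | power, linear ANCOVA |
|---|---|---|---|---|
| 0.3 | 0.65 | 0.62 | 65% | 82% |
| 0.5 | 0.75 | 0.72 | 77% | 88% |
| 0.7 | 0.85 | 0.81 | 93% | 96% |
| 0.9 | 0.95 | 0.91 | about 100% | about 100% |

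Against a comparison of mean change, a ratio of 0.65 is worth 1/0.65 − 1 = 54% more patients, 0.85 is worth 18%, and 0.95 is worth 5%.

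**Unequal variances.** At rho = 0.7 and r = 1.3: 1.69 × 0.51 / (1 + 1.69 − 1.82) = 0.862 / 0.870 = 0.99, almost no gain. At r = 0.8: 0.64 × 0.51 / (1 + 0.64 − 1.12) = 0.326 / 0.520 = 0.63, a larger gain.

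**Chance imbalance.** With r = 1, a baseline difference d between arms shifts the expected change contrast by rho·d − d = −(1 − rho)d. Adjustment removes this shift.

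**Non-normal scores.** Simulated power, again with 75 per arm, 0.4 SD and alpha 0.1. The ceiling case is a rounded score with mean 42 and SD 6, held within 12 to 48, the range of ISEL-12 and CASE-Cancer. The heavy-tailed case uses a t distribution with 3 df. The models adjusted for baseline only.

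| case | rho | rank-sum on change | linear ANCOVA | rank ANCOVA |
|---|---|---|---|---|
| ceiling | 0.3 | 61% | 79% | 79% |
| ceiling | 0.5 | 69% | 85% | 84% |
| ceiling | 0.7 | 85% | 93% | 92% |
| heavy tails | 0.3 | 82% | 85% | 96% |
| heavy tails | 0.5 | 92% | 89% | 98% |
| heavy tails | 0.7 | 99% | 96% | 99% |

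Rank ANCOVA equalled or beat the planned test in every case simulated, including the normal ones. Type I error lay between 8.4% and 11.5% for all methods, against a nominal 10%.

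**The case against.** The strongest reply is that the rank test was chosen for robustness. Section 9.4.1 foresees a normality check and nonparametric tests where suitable, and the heavy-tailed simulations bear this out: the planned test beats linear ANCOVA at rho 0.5 and 0.7. That stands. A reader might infer that the plan gives up precision for no return; the documents do not support this as to the rank step. The criticism reaches only the subtraction of baseline, because a rank-based or ordinal adjusted model keeps the robustness and still uses baseline.

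Other stronger readings also fail:

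- **Bias.** Regression to the mean operates in both arms, and chance imbalance averages to zero over randomizations. The planned test is valid, and it matches the endpoint as defined in Table 2.
- **Sole evidence on mechanism.** CTM-15 serves the same objective, and Section 9.4.9 also relates unresolved barriers to PORT delay.
- **No effect size at all.** Section 9.4.9 provides descriptive summaries and 90% CIs for means. What it lacks is an interval for the difference between arms.
- **A fixed gain of 15% to 35%.** This presumes rho between 0.3 and 0.7, equal variances and a comparison of means. The documents supply none of the quantities needed to check that.

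**Conclusion.** The point holds as an improvement in efficiency, not as the correction of an error. For the four scales with a screening baseline, the planned analysis is valid but usually less precise than a baseline-adjusted one. With equal variances and near-normal scores the adjusted analysis has about 0.62 to 0.91 of the variance of the planned test over rho 0.3 to 0.9. The gain is small when rho is high and can nearly disappear when follow-up variance exceeds baseline variance. With heavy tails the advantage requires a rank-based or similar robust form; an ordinary linear model can do worse than the planned test. The endpoints are exploratory, and no sample size, primary conclusion or secondary conclusion depends on them.

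**What to change.** In Section 9.4.9, make the between-arm analysis of ISEL-12, each Perceived Susceptibility subscale, IPQ-R Consequences and CASE-Cancer a model of the follow-up score on arm, baseline score, race and predicted radiation facility.

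- **Form.** Fix it in advance: rank-based or ordinal ANCOVA, or linear ANCOVA if normality is acceptable under Section 9.4.1. State the rule for that judgment before arms are compared.
- **Estimate.** Report the adjusted between-arm difference with a 90% CI. If a rank or ordinal model is chosen, say which effect measure is reported, since its coefficient is not on the score scale.
- **Visit.** Name the follow-up visit for Perceived Susceptibility and IPQ-R, which are assessed at Visits 3 and 4. The schedule's footnote omits Visit 4 for participants never discharged before PORT, so the choice affects who is analyzed.
- **CTM-15.** Compare arms adjusting for race and facility only, and name its visit too. Section 9.4.9 lists care coordination among the constructs compared before and after the intervention; that wording should be reconciled with the absence of a CTM-15 baseline.
- **Sensitivity.** Keep the rank-sum test on change as a sensitivity analysis.

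The cost is a change of SAP wording. It needs no new data, visits or patients.

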8.5 ADVERSE EVENTS AND SERIOUS ADVERSE EVENTS

8.5.1 DEFINITION OF ADVERSE EVENTS

This trial is considered to carry a low risk to subjects (i.e. has a "no more than minimal risk" designation). As such, this protocol defines an adverse event (AE) as any undesirable sign, symptom, medical, psychological, social, or emotional reaction that is definitely, probably, or possibly related to the study intervention (as described in 8.5.3). Post-surgical treatment toxicity (wound complications, hospital readmissions, etc) is expected for the NDURE and UC care groups and known to be associated with the primary endpoint (PORT delay).⁶⁰ Although it is not hypothesized that the NDURE intervention will decrease the risk of treatment toxicity, it is hypothesized that NDURE will improve patient-provider communication and care coordination about treatment toxicity, thereby decreasing the risk of PORT delay. As a result, data about expected post-surgical treatment toxicity (wound-healing complications, need for additional surgery, unplanned visits to the emergency room, and unplanned hospital readmissions) are assessed in the PBQ-P and PBQ-N (Section 8.4.5) to allow for specific comparison of these types of events between the NDURE and UC arms and their relationship with the primary endpoint (PORT delay).

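### The exploratory model linking unresolved barriers to PORT delay (section 9.4.9) has no term for trial arm, so in a pooled fit arm can confound the barrier coefficient

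*Combined protocol and SAP*

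**What the plan says.** Section 9.4.9 computes the proportion and number of unresolved barriers "at the end of NDURE, consistent with prior PN studies". It then fits a logistic regression "to assess the association between unresolved barriers and the rate of PORT delay (primary endpoint), controlling for randomization stratification variables". It does not say which arms or which analysis set enter the fit.

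The stratification variables are identified in section 9.4.3.2, where the primary model describes PORT delay "as a function of treatment arm and randomization stratification variables (race and predicted location of radiation facility". Arm and the stratification variables are separate terms there, so adjusting for the second does not bring in the first. No other section adds arm, an arm-by-barrier term or a separate fit by arm to the barrier model.

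The barrier endpoints belong to an exploratory objective in Table 2 (section 3): "To explore the preliminary clinical impact of NDURE compared with UC on decreasing barriers to timely PORT". Section 8.5.1 adds that post-surgical toxicity items are collected in the barrier questionnaires "to allow for specific comparison of these types of events between the NDURE and UC arms".

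**The concern.** The trial hypothesises that NDURE lowers PORT delay, and it explores whether NDURE lowers barriers. If both happen, usual-care patients tend to have more unresolved barriers and more delay, and NDURE patients fewer of each. A regression that pools the arms without an arm term attributes part of that between-arm contrast to barriers, even if patients with more barriers are no more likely to be delayed within either arm.

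NDURE has components that could shorten the time to PORT without changing a patient's barrier score. Under sections 6.1.1.1 and 6.1.1.2 (Table 3), the navigator alone makes PORT-related referrals and appointments, contacts pathology when a report is late, and tracks attendance. An effect by these routes is what would make the pooled coefficient misleading.

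What is at stake is the reading of one exploratory result: whether unresolved barriers go with delay among patients treated alike, or only because NDURE changed both.

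**Working it through.** **Inputs from the documents.** Delay is 45% in usual care and 25% in NDURE, with 75 patients per arm and a two-sided test at 0.1 (section 9.2.2). Allocation is 1:1, with 25 African American patients per arm (section 6.3). Each barrier score runs from 0 to 17 (section 8.4.5).

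**Inputs assumed.** The documents give no barrier counts or prevalences, so these are varied below.

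**Step 1: reproduce the plan's own figure.** The plan states no figure for the barrier model, but it does state 83% power for the primary comparison.
- Pooled SE = √(2 × 0.35 × 0.65 / 75) = 0.0779.
- Unpooled SE = √((0.45 × 0.55 + 0.25 × 0.75) / 75) = 0.0762.
- z = (0.20 − 1.645 × 0.0779) / 0.0762 = 0.94, so power is 82.7%. The delay inputs are being read as intended.

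**Step 2: closed form for a yes/no barrier.** Let b0 and b1 be the proportions with any unresolved barrier in usual care and NDURE, with no barrier–delay association inside either arm. With equal arms,
- P(delay | barrier) = (0.45·b0 + 0.25·b1) / (b0 + b1)
- P(delay | no barrier) = (0.45·(1 − b0) + 0.25·(1 − b1)) / (2 − b0 − b1)

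For b0 = 0.60 and b1 = 0.40 these are 0.37 and 0.33. The pooled odds ratio is (0.37/0.63) / (0.33/0.67) = 1.19, although the true within-arm odds ratio is 1.

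| Assumed prevalence, usual care / NDURE | Pooled odds ratio |
|---|---|
| 60% / 60% | 1.00 |
| 60% / 50% | 1.09 |
| 60% / 40% | 1.19 |
| 60% / 30% | 1.30 |
| 70% / 20% | 1.56 |

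**Step 3: simulation with a barrier count.** There are 75 patients per arm and 3,000 simulated trials per scenario. Counts are Poisson and independent of delay within arm. Race and facility are given small effects on delay, and facility is assumed to split evenly. The logistic regression is on barriers, race and facility, as the plan has it.

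| Assumed mean barriers, usual care / NDURE | Median OR per barrier | p < 0.05 | p < 0.10 |
|---|---|---|---|
| 3 / 3 | 1.00 | 5% | 10% |
| 2.5 / 2.25 | 1.02 | about 6% | about 11% |
| 3 / 2.5 | 1.04 | 6% | 12% |
| 2.5 / 2 | 1.05 | 7% | 14% |
| 3 / 2 | 1.09 | 13% | 21% |
| 3 / 1.5 | 1.13 | 21% | 32% |
| 2.5 / 1 | 1.15 | 23% | 33% |
| 3 / 1 | 1.16 | about 32% | about 44% |

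Repeat runs differ by a few percentage points at most.

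**Step 4: add arm.** With arm in the model the odds ratio is 1.00 per barrier, and rejection is close to 5% and 10% in every scenario.

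**Step 5: check the condition.** If NDURE changes only one of the two variables (barriers 3 versus 3, or delay 35% versus 35%), the model without arm gives an odds ratio of 1.00 and nominal error. Both effects are needed for the bias.

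**The case against.** **The fit may not be pooled.** The reference to the end of NDURE could mean the NDURE arm only. Section 6.2.1 has the NDURE navigator log barriers and the actions taken on them, and under section 6.1.1.2 the usual-care nurse navigator stops after the initial consultation. In an NDURE-only fit arm cannot confound. Pooling remains the more natural reading: the objective is a comparison with usual care, Table 1 covers both arms and schedules the questionnaires, and section 8.5.1 compares their items between arms. The ambiguity stands and should be removed.

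**The association could be real.** If NDURE reduced delay only through the measured barriers, the pooled association would not be spurious. That is correct, so the concern is conditional.

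**The arm difference in barriers may be small.** Section 8.5.1 says the questionnaires include toxicity items and that NDURE is not expected to reduce toxicity. This argues against assuming a large gap in the total count. At 2.5 versus 2.25 the error is close to nominal.

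**The threshold is unclear.** Section 9.4.1 sets a two-sided p-value of 0.05 alongside 90% intervals, and section 9.4.9 states no level for this model. Both levels are therefore shown.

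**Adjustment does not deliver mechanism.** The last barrier questionnaire falls at Visit 5, after PORT starts or at 12 weeks if it never does (section 1.3). Delay status is settled by then, so an arm-adjusted coefficient is still only an association.

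**A stronger reading to resist.** A reader might infer that the protocol relies on this model to answer its worry about non-specific effects in section 4.2.2. The documents do not support that. Section 4.2.2 points to behavioural mechanisms, and Table 2 and section 8.4.7 assign those to the CTM-15, ISEL-12, Perceived Susceptibility, IPQ-R Consequences and CASE-Cancer scales. Barriers sit under a different exploratory objective, and section 9.4.9 claims only an association.

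**Conclusion.** The omission is real: section 9.4.9 adjusts for race and predicted facility only. Confounding by arm follows if both arms are pooled and NDURE lowers barriers and also lowers delay at least partly by routes other than the measured barriers. It is not certain to occur.

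Over the assumed barrier gaps the spurious odds ratio is about 1.02 to 1.16 per barrier, with false-positive rates of about 6% to 32% at 0.05 and 11% to 44% at 0.10. These ranges depend on barrier means that the documents do not give, on Poisson counts, on the planned 45% and 25% delay rates, and on complete data for 75 patients per arm. No single value in the range should be read as the plan's error rate.

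This is a minor point about one exploratory model.

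**What to change.** In section 9.4.9, add trial arm as a covariate to the barrier–delay logistic model, report the barrier coefficient with and without it, and state that both arms are included. Naming the analysis set in the same sentence would remove the remaining ambiguity. Describe the result as an exploratory association, not as evidence of mechanism.

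The cost is one covariate and a sentence of text, with no new data, visits or patients: a free improvement.
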